2.2 Main trial objectives

2.2.1 Clinical aims and objectives

The primary objective of the trial is to determine whether BCG vaccination reduces rates of moderate-severe AECOPD over 12 months in patients who have a clinical diagnosis of COPD, and a history of exacerbation in the preceding year. Our hypothesis is that the vaccine will reduce infectious exacerbations, and that there may be a greater effect for viral driven events.

The secondary clinical objectives are to compare the rate of hospitalisations for infective exacerbations, QOL, total number of days of antibiotic and steroid therapy use during the follow up period between intervention and control groups and to determine the acceptability of the BCG vaccine.

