8.2.2 Secondary outcomes

We will compare the following between intervention and control groups over 12 months follow up from IMP administration date (or after the date of randomisation if no treatment was administered), unless otherwise stated.

- Hospitalisation rate for infective exacerbations equivalent to the rate of severe AECOPD.
- Quality of life (QOL), as defined by the COPD Assessment Test (CAT)

- Total number of days of antibiotic therapy for AECOPD during follow up, defined by patient self-report at each event, and confirmed by the site in the medical record (section 8.1).
- Total number of days of oral steroid therapy for AECOPD during follow up, defined by patient self-report at each event, and confirmed by the site in the medical record (section 8.1).
- Type of exacerbation (as they occur (rate over time)):
 - Defined by Anthonisen criteria, collected at AECOPD using patient self-report of symptoms. Type 1 being characterised by increased breathlessness, sputum volume and sputum purulence, type 2 by two of these three symptoms and type 3 by a single symptom.
 - Defined by the clinical adjudication committee (CAC), who will use sputum, viral and symptom data to determine aetiology of each event, categorising events as infectious (confirmed bacterial, confirmed viral, clinically likely but no organism identified) and non-infectious.

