14.2.3 Secondary outcome estimands

Estimands for the secondary outcomes will deal with intercurrent events as per the primary estimand. All analysis models will adjust for the minimisation variables listed in Section 6.6. The differences between groups for the secondary outcomes will be presented along with 95% confidence intervals. Incidence rate outcomes (e.g. the hospitalisation rate for infective exacerbation

of airways disease at 12 months) will be analysed as per the primary outcome using negativebinomial regression models incorporating exposure time (person-years). Count outcomes (e.g. total number of days of antibiotics for AECOPD, total number of days of oral steroid therapy for AECPOD) will be analysed using Poisson regression models to calculate adjusted incidence rate ratios, unless there is compelling evidence of overdispersion, in which case negative-binomial regression models will be used. The chosen model will incorporate exposure time (person-years). The continuous secondary QOL outcome (using the CAT score) will be analysed using mixed effects linear regression models to calculate an adjusted mean difference accounting for the collection of QOL at multiple time points. Ordinal outcomes (e.g. type of exacerbation classified using two different approaches: i) a three-level classification based on Anthonisen criteria, and ii) a four-level classification based on clinical adjudication) will be analysed using mixed effect ordinal regression models to estimate the adjusted odds ratios.

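### The adjudicated cause of exacerbation has four unordered categories and is defined as a rate, but the protocol fixes an ordinal regression odds ratio for it

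*Protocol*

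**What the plan says.** Section 8.2.2 introduces the outcome as "Type of exacerbation (as they occur (rate over time" and gives two versions of it. One is the Anthonisen type. The other is set by the clinical adjudication committee, "who will use sputum, viral and symptom data to determine aetiology of each event", with the result "categorising events as infectious (confirmed bacterial, confirmed viral, clinically likely but no organism identified) and non-infectious". No order among these four levels is stated.

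Section 14.2.3 then calls both versions ordinal outcomes and fixes their analysis. For the committee's version it reads: "a four-level classification based on clinical adjudication) will be analysed using mixed effect ordinal regression models to estimate the adjusted odds ratios". For incidence rate outcomes the same section prescribes something else: they "will be analysed as per the primary outcome using negativebinomial regression models incorporating exposure time (person-years").

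The hypothesis, in sections 1.2 and 2.2.1, is about numbers of events by cause: "Our hypothesis is that the vaccine will reduce infectious exacerbations, and that there may be a greater effect for viral driven events".

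**The concern.** An ordinal model needs levels that can be ranked. One could rank some of these four by certainty of infection, but no such ranking separates confirmed bacterial from confirmed viral. Someone must nevertheless choose an order before the model can be fitted, and the answer then depends on that choice. If it is made late, it could favour either direction.

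The summary measure also does not match the outcome. The outcome is a rate over time; the planned result is an odds ratio with no exposure time attached. Since every level describes an exacerbation, a participant with none seems to contribute nothing. The comparison is then of case mix among events that arise after randomisation, rather than of event rates in the randomised groups.

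At stake is the one clinical outcome in the protocol that separates viral from other exacerbations. The mechanism the trial proposes would show here, and the planned model does not estimate it.

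**Working it through.** **1. The protocol's own figure.** No figure is stated for this outcome. The size of 361 per group used below comes from section 14.1 and reproduces. With rates 2.25 and 1.8, k = 0.36, one year, two-sided 5% and 90% power:

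- n = (z_α√V0 + z_β√V1)² / (ln 0.8)²
- V0 = 2/2.025 + 2(0.36) = 1.708, using the pooled rate
- V1 = 1/2.25 + 1/1.8 + 2(0.36) = 1.720
- n = (1.960 × 1.307 + 1.282 × 1.311)² / 0.0498 = 361.4

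**2. Illustration of order dependence.** The protocol gives no shares by cause, so these are assumed: control mix 30% bacterial, 30% viral, 25% clinically likely, 15% non-infectious; BCG halves viral events and changes nothing else.

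- Control events: 361 × 2.25 = 812.25, that is 243.7 / 243.7 / 203.1 / 121.8.
- BCG events: 243.7 / 121.8 / 203.1 / 121.8, total 690.4. Overall rate ratio 690.4/812.25 = 0.85.
- BCG mix: 35.3 / 17.6 / 29.4 / 17.6%.
- Viral rate ratio: 121.8/243.7 = 0.50, whatever the order.

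A proportional-odds model was fitted by maximum likelihood to these expected counts, without random effects or covariates. An odds ratio above 1 means a shift towards later levels under BCG.

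| Level order | Odds ratio |
|---|---|
| bacterial, viral, likely, non-infectious (as listed) | 1.06 (p = 0.54) |
| bacterial, likely, viral, non-infectious | 0.79 |
| likely, viral, bacterial, non-infectious | 1.12 |
| viral first, others in any order | 1.49 |
| viral last, others in any order | 0.67 |

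The last two rows are one fit read in opposite directions (1/1.49 = 0.67). The first two rows are not: both run from bacterial to non-infectious, and exchanging the two middle levels moves the estimate across 1.

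**3. Other assumed mixes, viral halved.**

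| Control mix | Listed order | Viral last / viral first |
|---|---|---|
| 25/25/25/25% | 1.12 | 0.71 / 1.41 |
| 30/30/20/20% | 1.06 | 0.67 / 1.49 |
| 25/20/30/25% | 1.11 | 0.75 / 1.33 |

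**4. A uniform effect.** If BCG cuts every cause by 20%, the design effect in section 14.1, the mix is identical in both arms and the odds ratio is 1.00 in every order. This is correct as a statement about mix and silent about rates.

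**5. Who would contribute.** Under the protocol's rates and k, the share with no event is (1 + k·r)^(−1/k): (1.81)^(−1/0.36) = 0.19 in control and (1.648)^(−1/0.36) = 0.25 under BCG. These participants would be absent from a model of events only.

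**6. What rates by cause would offer.** Power = Φ(|ln RR| / √(V/361) − 1.96), with V = 1/r0 + 1/(r0·RR) + 2k. Assuming viral events are 20–30% of 2.25 per year and k is 0.36–1.5, power is about 99% or more for a viral rate ratio of 0.5, about 90–99% for 0.6, and about 32–56% for 0.8.

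**The case against.** Several counter-arguments have force.

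- **Secondary outcome.** It touches neither the primary analysis nor the sample size, and exacerbation type is not named among the secondary objectives in section 2.2.1. The viral effect is worded tentatively ("there may be a greater effect for viral driven events"), and the protocol nowhere says this model is its test. That stands and limits the severity.
- **Illustrative figures.** The shares are assumed, the fit omits the planned random effect and covariates, and a halving of viral events with no other effect is narrower than the stated hypothesis. The protocol also does not say proportional odds. All of this stands, so p = 0.54 is not the planned analysis's p-value. None of it supplies an order that the categories lack.
- **0.67 to 1.49 as a range.** A reader might take this as the model's instability. The two ends are the same fit reversed. In absolute size the estimate varies from 1.06 to 1.49, with a change of direction when viral moves between inner positions.
- **Events only.** The protocol does not state this; it is inferred from the levels and from the absence of exposure time. Event mix is a legitimate descriptive question when total rates are estimated elsewhere, but it is not the rate that section 8.2.2 defines.
- **Anthonisen types.** A reader might extend the criticism to them. Types 1 to 3 are ranked by number of symptoms, so an ordinal model is admissible there, and preferring rates would be a choice of estimand.
- **Hospitalisation.** Section 8.2.2 also lists "Hospitalisation rate for infective exacerbations equivalent to the rate of severe AECOPD". Whether those two rates can be equal is a separate question of definition and gives no support to this point.

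**Conclusion.** The analysis is wrong as written for the adjudicated classification: an unordered outcome defined as a rate is given an ordinal odds ratio. The protocol itself fixes the model, so this is not a detail left to the SAP. It should be fixed, but as a secondary-outcome matter.

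That the categories are nominal and that the measure does not match the definition follow directly from sections 8.2.2 and 14.2.3. That only events contribute is a strong inference. The magnitudes depend on the assumed mix and the simplified fit. In the mixes tried, with a true viral rate ratio of 0.50, the listed order gives 1.06 to 1.12.

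Two stronger conclusions are not supported: that the odds ratio can never carry information (with viral at one end it does register a shift in mix), and that the trial's main conclusion is at risk.

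**What to change.** In section 14.2.3, remove the four-level adjudicated classification from the ordinal outcomes. Analyse it with negative binomial models of each participant's count, with exposure time and the minimisation variables, giving an incidence rate ratio for viral, bacterial, clinically likely, non-infectious and all infectious events. If the mix of events is also of interest, use a multinomial model and label it descriptive. The ordinal model may stay for the Anthonisen types. Settle this before any comparison by arm.

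The cost is a wording change: the data are already to be collected and the model family is already in the section.

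There are two drawbacks. Five rate ratios replace one odds ratio, and section 14.2 makes no multiplicity adjustment, so they should be read as a set of secondary estimates. Confirmed counts also depend on samples being returned, which is voluntary (section 7.3) in a trial where participants know their allocation (section 6.5). Section 17.5 expects about 1300 sampled exacerbations, against 361 × (2.25 + 1.8) = 1462 under the design rates. Sample return should therefore be reported by arm beside the rate ratios.

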14.2.4 Planned subgroup analyses

Subgroup analyses will be performed on the primary estimand only and limited to age (<65 or ≥65 years) and prior BCG vaccination or TB infection and performed on the primary outcome only. The effects of these subgroups will be examined by including an intervention group by subgroup interaction parameter in the regression model, which will be presented alongside the effect estimate and 95% confidence interval within subgroups. The results of these pre-specified subgroup analyses will be treated with caution and will be used for the purposes of hypothesis generation only.

14.2.5 Missing data and sensitivity analyses

Every attempt will be made to collect full data to the end of the study on all study participants; it is thus anticipated that missing data will be minimal. Participants will be included in the primary analysis up to the time point they were last followed up. If no primary outcome data will be collected for a participant, they will not be included in the primary analysis in the first instance. This presents a risk of bias, and sensitivity analyses will be undertaken to assess the possible impact of the risk. This will consist of simulating the missing responses using a multiple imputation approach. Parameters used to simulate the missing responses will include the minimisation variables, intervention group, exposure time (person-years), and, if applicable, previous response at each time point. Full details will be included in the Statistical Analysis Plan.

14.3 Planned final analysis

The primary analysis for the trial will occur once all participants have completed the planned 12month follow-up assessment and corresponding outcome data has been entered onto the trial database and validated as being ready for analysis.

15. HEALTH ECONOMICS

No Health Economic evaluation is planned for this trial.

16. QUALITATIVE ACCEPTABILITY STUDY

This is a trial of the world's most used vaccine, but it is not being given for traditional vaccine reasons, in that it is not being used to prevent TB, but to prevent more general infections (exacerbations) in COPD. The putative mechanism also differs from normal vaccines, so patients' understanding of this may be lower and thus take up of the vaccine in real-life might be poor. The aims of the acceptability work are to explore the understanding and acceptance of vaccines in

general, and of this specific vaccine, exploring and comparing uptake/acceptability to other exacerbation prevention strategies, for both patients and healthcare professionals. For example, patients may accept SARS-CoV2 vaccine to prevent coronavirus disease (COVID-19), or flu vaccine to prevent flu, but may have difficulty understanding BCG is being given for reasons other than TB. However, they take other medicines that are for generic infection/exacerbation prevention (e.g. macrolides (30), inhalers (22), so exploring their understanding of this concept, in the context of acceptability of the intervention would be relevant. Methods to enhance uptake will also be pertinent to elicit, and findings may be generalisable to other respiratory vaccines. We have systematically reviewed factors aimed at increasing vaccine uptake in COPD (37), and found that multimodal interventions, which target multiple aspects of evidence-based care and use both patient-focussed and clinician-focussed techniques, may have the greatest impact on vaccination rates. This will inform our topic guide, alongside the general literature (38) and patient and public involvement (PPI) input.

Data will be collected using individual interviews with up to 25 patients (including those who decline participation in the trial) and 15 healthcare professionals (HCPs). Interviews will be conducted virtually using an UoB approved platform account, on the telephone or by Voice Over Internet Protocol (VOIP) (e.g. Teams) and audio recorded using an encrypted voice recorder or the recording facility of the participants' chosen VOIP platform. All recordings will be transferred to one of the University of Birmingham's approved digital storage systems e.g. One drive.

Recordings will be transcribed clean verbatim by an external transcription service. Participant data files will be encrypted and transferred to the external transcription company via a University of Birmingham approved secure data transfer link e.g. Sharepoint. The transcription company will sign a full and comprehensive confidentiality agreement. Transcripts will be given an ID number by the qualitative team prior to transfer; transcribers will have not have access to any personal data regarding interviewees. No transcripts or recordings will be stored locally by the external transcription service. Transcripts will be stored on the University's secure cloud-based server.

Data will be managed and analysed using the Framework method. Interpretation of the data will draw on relevant theoretical concepts of risk work in the public encounter (to understand HCPs experiences of managing conversations about vaccines, vaccine hesitancy and preventative interventions generally) and organisational and interpersonal trust in relation to prevention and preventative interventions (to understand patient's responses) (39-42).

Those declining to participate in the main trial will have the option to express their views in an interview as described above. Alternatively, they can complete a brief survey either included in their invitation to participate in the main trial or provided directly by the research team e.g. in response to published adverts. Responses will be recorded on paper, online or over the phone. Before the survey is completed, patients will be informed that it is a one-off survey and that they are free to discontinue the survey at any point without their care being affected. Consent will be implicit by virtue of the fact that: a) they have chosen to contact us and b) that they choose to answer the questions. The researcher will not have access to any identifiable data from those completing the survey.

17. MECHANISTIC STUDY

17.1 Background

Briefly, the main study provides an oversight of the effects of BCG vaccination on a large population over time through a minimally invasive approach and correlation with clinical outcomes. Advantages include ease of unbiased sampling in the whole study population, simple processing, ability to detect specific anti-BCG responses, as well as general effects of vaccination on the host and the ability to revisit archived samples when other effects are identified. Collectively, the detailed mechanistic substudy gives comprehensive assessment of BCG vaccine-specific responses, trained immunity, gene expression analyses, cell phenotyping and functional screening, thus enabling us to provide mechanistic insights into how BCG may modulate the host over the course of this study. Our experimental approach in the sub-study is focused to capture multiple aspects of immune responses in terms of relative "complexity". Thus, within our approach we can identify differences in soluble factors (e.g. antibodies, cytokines), epigenetic changes, gene expression and cellular phenotypes. This will allow integration across readouts captured from various platforms.

The mechanistic analysis will provide a comprehensive assessment of BCG vaccine-specific responses through differences in soluble factors (e.g. antibodies, cytokines), trained immunity, gene expression analyses, cell phenotyping and functional screening. Collectively, this will enable us to provide mechanistic insights into how BCG may modulate the host over the course of this study.

17.2 Objectives

To develop mechanistic insights into how BCG can modulate the risk of airway disease exacerbation.

17.3 Methods

The mechanistic study consists of 3 tiers of testing:

- 1. Dried blood spot (DBS) sampling of all patients to assess humoral immunity.
- 2. Detailed mechanistic sub-study on 80 participants that involves more thorough assessment of humoral immunity by means of venepuncture.
- 3. Exacerbation sampling captures microbiological and immunological information at the start of exacerbations via patient submitted samples sent by post to the Clinical Immunology Service at the University of Birmingham.

All patients enrolled in the main study will have consented to provide DBS and exacerbation samples, and the 80 participants in the detailed mechanistic sub-study will be drawn from those who opt in at consent. Participants who gave consent to join the Mechanistic sub-study and were selected to take part will be notified by a letter. Local site team will contact those participants to arrange for one, three- and twelve-months visits.

The tiers are summarised in Figure 1 through a flow diagram that indicates the anticipated number of subjects sampled, the nature of the samples obtained and the assessments that will be made for each sample. More details on the tiers methods are included in Appendix A.

Figure 1. Laboratory plan for Tier 1-3 samples

Flow diagram of the laboratory plan for Tier 1-3 samples collected during STABILISE. n=800 has been shown for tier 1, though n=804 altogether, assuming a small rate of sample failure.

17.4 Outcomes

Mechanistic outcomes will be explored between individuals according to demographic and relevant minimisation data (e.g. prior TB vaccination), and as change from baseline in an individual.

17.4.1 Tier 1 outcomes (all cohort 800 participants)

All outcomes will be recorded at the pre-randomisation baseline visit and then at 1, 3 and 12 months post randomisation/vaccination (for the control/BCG vaccine groups respectively)

- Anti-BCG antibody responses, as obtained from ELISAs to detect IgG, IgA and IgM responses to whole BCG organism, proteinaceous (Ag85) and a non-proteinaceous (Lipoarabinomannan) antigen
- Cytokines: IL-1B, IL-6, TNFα and IL-10

17.4.2 Tier 2 outcomes (80 participants)

All outcomes will be recorded at the pre-randomisation baseline visit and then at 1, 3 and 12 months post randomisation/vaccination (for the control/BCG vaccine groups respectively)

- Antigen-specific B cell responses to BCG
- BCG antigens and relevant pathogens

- measures of trained immunity as determined by histone markers and heterologous cellular responses
- transcriptomics
- leukocyte, T and B cell phenotypes

17.4.3 Tier 3 outcomes (all exacerbations)

All outcomes will be recorded whenever a participant experiences an exacerbation and provides sputum, saliva, nose/throat swabs, and DBS samples.

Anti-BCG antibody responses, as obtained from ELISAs to detect IgG, IgA and IgM responses to whole BCG organism, proteinaceous (Ag85) and a non-proteinaceous (Lipoarabinomannan) antigen

- Cytokines: IL-1B, IL-6, TNFα and IL-10
- Type of pathogen present (bacteria, virus) and specific species
- IgG and IgA response to any identified pathogen

17.5 Sample Size

Tier 1 will consist of the whole cohort of 804 participants as for the main RCT.

Tier 2 will consist of the first 80 participants who have consented to provide samples for the detailed sub-study. Since consent to participate in the detailed mechanistic sub-study is a minimisation criterion, these 80 participants will be well balanced in terms of allocated treatment arm and the other minimisation criteria (see Section 6 – enrolment, randomisation and blinding).

Tier 3 will consist of all participants who experience an exacerbation and provide sputum, saliva, nose/throat swabs and DBS samples. We anticipate we will collect data on around 1300 exacerbations from the 804 participants.

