6.6 Randomisation method

Participants will be randomised at the level of the individual in a 1:1 ratio to either BCG vaccine or no vaccine via a central secure web-based EDC system. A minimisation algorithm will be used within the randomisation process to ensure balance in the BCG vaccine allocations over the following variables:

- Age (<65 or ≥65 years)
- Prior BCG vaccination or TB infection (yes/no)
- Consent to participate in the detailed mechanistic sub-study (yes/no)
- Site

To avoid the possibility of the intervention allocation becoming predictable, a random element will be included in the algorithm. Full details of the randomisation specification will be stored in a confidential document at BCTU.

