17.6 Analysis of Outcomes

Analyses of mechanistic outcomes will be largely exploratory and completed by the laboratory team. In each Tier, summary measures of readouts from samples will be provided: means and SDs, or medians and IQRs as appropriate. Summaries will be reported separately for each time point and each treatment group, as well as pooled across treatment groups.

Subsets of sample readouts to include in the statistical models will be determined through clinical opinion and principal component analysis (PCA). Across the tiers, the longitudinal trajectories of the sample readouts will be analysed through linear mixed effects models. Associations between longitudinal samples and exacerbation rates will be explored through negative binomial mixed effects models. Model based estimates of time and treatment effects will be reported along with 95% confidence intervals and p-values from two-sided tests. Visual plots of fitted values will be provided to aid interpretation.

In Tier 2, additional analysis, through linear mixed effects models, will explore the associations between the DBS elute antibodies collected in Tier 2 and those in Tier 1. These analyses will include any new metabolites identified in Tier 2.

Associations between immune responses to BCG vaccination and exacerbations will be explored through negative binomial mixed effects models. Model based estimates of time and treatment

effects will be reported along with 95% confidence intervals and visual plots of fitted values to aid interpretation.

Exploratory identification of risk factors for exacerbation (classed as a binary yes/no outcome) will be performed using logistic regression modelling. Candidate predictors identified from clinical expertise and through analysis of samples in Tier 3 (and potentially Tiers 1 and 2) will be included in the model. Model performance will be reported through the C-index and Brier score. Calibration slopes will be plotted. Model overfitting will also be estimated, and optimism-adjusted estimates will be produced.

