In this detailed mechanistic subgroup, we propose to undertake an in-depth study in the first 80 participants (50:50 vaccine: no vaccine) who have consented to provide samples for the detailed mechanistic study. Since consent to participate in the detailed mechanistic sub-study is a minimisation criterion, these 80 participants will be well balanced in terms of allocated treatment arm and the other minimisation criteria (see Section 6 – enrolment, randomisation and blinding). We will collect the following blood samples: whole blood, peripheral blood mononuclear cells (PBMC), neutrophils, serum and PAXgene tubes. Participants will have approximately 75ml of blood taken at each visit. This cohort will also provide samples at the pre-randomisation baseline visit and then at months 1, 3 and 12 months post randomisation/vaccination (for the control/BCG vaccine groups respectively). These blood samples will be compared to the DBS samples from the Tier 1 cohort and the exacerbation samples from the Tier 3 cohort. The following analyses will be conducted:

- Antigen-specific B cell responses to BCG, BCG antigens and relevant pathogens. ELISAs to detect BCG-specific responses will be performed as for the main study alongside IgG isotype analysis, since in previous studies we identified an inverse correlation between IgG2 responses to BCG in infants and risk of a positive test for latent TB infection (46). Coupled to this we will perform ELISPOTs to determine Bmem responses by our standard approaches. Where relevant, if pathogens are identified in the exacerbation samples, this analysis will be expanded to assess antibody responses to these organisms +/- other pathogens. Such tests will be guided by whether any pathogens are identified in the exacerbation samples.
- Assessment of trained immunity via histone markers and heterologous cellular responses. In addition to cytokine measurements, innate immunity will be assessed in vitro via methylation and acetylation modifications of specific histone markers at loci of proinflammatory genes. This will be performed using standard approaches at the Birmingham Centre for Genome Biology (47). Briefly, key cells (e.g. monocytes) will be isolated then fixed, sonicated and immunoprecipitated using antibodies against key histone targets (e.g.

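### Minimising on sub-study consent balances treatment arms among the 80 Tier 2 participants, but it does not support the stated balance on age and prior BCG/TB

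*Protocol*

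**What the plan says.** Section 6.6 describes the allocation: "A minimisation algorithm will be used within the randomisation process to ensure balance in the BCG vaccine allocations over the following variables". The list is age (under 65, or 65 and over), prior BCG vaccination or TB infection, consent to the detailed mechanistic sub-study, and site. It adds that "a random element will be included in the algorithm" and keeps the full specification confidential.

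Section 17.5 defines the sub-study: "Tier 2 will consist of the first 80 participants who have consented to provide samples for the detailed sub-study". It then gives consent's place among the minimisation criteria as the reason that "these 80 participants will be well balanced in terms of allocated treatment arm and the other minimisation criteria". Appendix A1.2 repeats the reasoning and gives the arm split as 50:50.

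Section 17.6 plans linear mixed models of the longitudinal readouts, done by the laboratory team and described as mostly exploratory. It says: "Model based estimates of time and treatment effects will be reported along with 95% confidence intervals and p-values from two-sided tests". It names no covariates. Section 17.4 says mechanistic outcomes will be explored by demographic and minimisation data and gives prior TB vaccination as its example. Section 14.2, on the main trial, sets a general rule of adjusting intervention effects for the minimisation variables and baseline values where this can be done.

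**The concern.** Minimisation over separately listed factors controls the arm totals within each level of each factor, taken one at a time. Consent as one such factor keeps BCG and control numbers close among consenters. It does not control how a second factor, such as prior BCG/TB, is split between arms inside the consenting group. The first half of the sentence in 17.5 follows from the reason given; the second half does not.

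Tier 2 measures BCG-specific B cell responses and trained immunity, and prior mycobacterial exposure is the minimisation factor that section 17.4 itself picks out for such readouts. A reader told that the 80 are balanced on it has little reason to check or adjust. A chance difference in previous exposure could then be read as part of a treatment effect reported with a confidence interval and p-value.

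**Working it through.** **1. Why the inference fails.** An illustration with 402 per arm and about 70% prior BCG/TB:

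| Group | BCG: prior yes / no | Control: prior yes / no |
|---|---|---|
| Consenters (40 v 40) | 32 / 8 | 24 / 16 |
| Non-consenters (362 v 362) | 248 / 114 | 256 / 106 |
| All (402 v 402) | 280 / 122 | 280 / 122 |

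Both margins are perfectly balanced: consent 40 v 40 and 362 v 362, prior BCG/TB 280 v 280 and 122 v 122. Inside the sub-study, prior BCG/TB is 32/40 = 80% v 24/40 = 60%, a gap of 20 points. Marginal minimisation has no reason to avoid this table.

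**2. Inputs for the size.** From the protocol: 80 sub-study participants, 50 sites, 1:1 allocation, four separate factors and a random element. Assumed, because the protocol does not give them: equal weights; probability 0.8 of the better-balancing arm (1.0 also run); age 65 or over in 50-80%; prior BCG/TB in 50-85%; several consent patterns. At least 80/804 = 10% must consent to fill Tier 2. Section 5.4 offers the sub-study only at selected sites, so a minority is plausible but not stated.

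**3. The plan's own figure, the 50:50 split.** It is reproduced. Among the 80, the mean difference in arm size is about 0.4-1.2 participants (95th percentile 2-4), against about 7 (95th percentile 16-18) under simple randomisation.

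**4. Age and prior BCG/TB.** Probability that the arms of the 80 differ by more than 10 points on at least one of the two. The three values in each cell are for prevalences (age 65 or over / prior BCG/TB) of 0.50/0.50, 0.65/0.70 and 0.80/0.85, with 1,000 runs each and assignment probability 0.8:

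| Share of cohort consenting | Separate margins | Simple randomisation | Minimised within consent strata |
|---|---|---|---|
| 12% (10 of 50 sites, 60% consent) | 0.54, 0.49, 0.35 | 0.60, 0.56, 0.41 | 0.02, 0.03, 0.01 |
| 20% (all sites) | 0.54, 0.46, 0.30 | 0.61, 0.55, 0.42 | 0.01, 0.02, 0.01 |
| 50% (all sites) | 0.39, 0.31, 0.19 | 0.60, 0.56, 0.44 | 0.01, 0.02, 0.02 |
| 90% (all sites) | 0.07, 0.05, 0.03 | 0.58, 0.56, 0.37 | 0.01, 0.01, 0.01 |

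For consent up to about 20%, a difference above 20 points on at least one factor occurs in about 2-9% of trials, and the mean difference on each factor is about 6-8 points, against about 3 when minimised within consent strata.

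**5. Hand check of the comparator.** Under simple randomisation with 40 v 40, SD of the difference = √(2p(1−p)/40). At p = 0.50 this is 0.112, so P(>10 points) = 2[1−Φ(0.894)] = 0.371 per factor and 1−(1−0.371)² = 0.60 for either. At p = 0.80 and 0.85 the SDs are 0.089 and 0.080, the per-factor probabilities 0.264 and 0.210, and 1−0.736×0.790 = 0.42 for either. Both agree with the table.

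**6. Site.** Site is partly protected when few sites take part. With six sites where everyone consents, the summed arm imbalance over sites is about 9, against 17.5 under simple randomisation.

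**The case against.** Much can be said for the plan. The arm half of the sentence is right, and site may be fairly balanced. The confidential specification might minimise within consent strata, which would make the claim true. The size depends on an unstated consent rate and on a 10-point threshold (4 people of 40) that is a reviewer's choice. Nothing in the trial's primary result depends on Tier 2. All of this stands. It does not rescue the printed argument, though: the only reason given is that consent is one of the criteria, and that reason does not deliver the second half.

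Four stronger readings are tempting, and the documents do not support them.

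- **Tier 2 effects will be unadjusted.** A reader might infer this from the silence of 17.6. But the rule in 14.2 covers minimisation variables and baseline values, 17.4 brings minimisation data into the mechanistic outcomes, and the SAP may settle the matter. What remains is an ambiguity: 14.2 sits in the main-trial section, and 14.2.1 and 14.2.3 name the adjustment for their own models while 17.6 does not. Exploring outcomes by a factor is also not the same as adjusting the treatment effect for it.
- **The analysis wastes precision through change scores.** The words "and as change from baseline in an individual" in 17.4 might suggest so. But 17.6 specifies mixed models of trajectories, which can use the baseline measurement efficiently.
- **Tier 1 shares the defect.** Tier 1 is the whole minimised cohort of 804, and no defect is shown there.
- **The comparison is biased.** Allocation is still randomised. An imbalance would be by chance, and the standard errors allow for chance.

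**Conclusion.** The concern holds in limited form. On the method as section 6.6 lists it, the balance statement in 17.5 and A1.2 is supported for treatment arm and partly for site, but not for age or prior BCG/TB. If about 10-20% of the cohort consents, the chance of a difference above 10 points on at least one of these is about 30-55%, little better than simple randomisation. It falls to about 20-40% at 50% consent and 3-7% at 90%, so the statement is close to true only if nearly everyone consents. These figures assume equal-weight minimisation on separate margins, an assignment probability of about 0.8 and the prevalences given above. The consequence is modest: a misplaced assurance about a largely exploratory sub-study, with no effect on the primary analysis.

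**What to change.** In 17.5 and A1.2, limit the sentence to balance in treatment arm. If the confidential specification does minimise within consent strata, say so instead, since that would justify the wider claim.

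In 17.6, state that Tier 2 treatment effects are adjusted for age group, prior BCG/TB and the baseline value of the same readout, in line with the general rule in 14.2.

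The cost is a few words of protocol text. All three covariates are already collected, and neither allocation nor sample size changes.
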